7.0 ASSESSMENT OF SAFETY

7.1. Safety Parameters

7.1.1.1 Definition of adverse events

The International Conference on Harmonization (ICH) Guideline for Good Clinical Practice (GCP) E6 (R1) defines an AE as:

Any untoward medical occurrence in a patient or clinical investigation subject administered a pharmaceutical product and which does not necessarily have a causal relationship with this treatment. An AE can therefore be any unfavorable and unintended sign (including an abnormal laboratory finding), symptom, or disease temporally associated with the use of a medicinal product, whether or not considered related to the medicinal product.

An AE includes but is not limited to any clinically significant worsening of a subject's pre-existing condition. An abnormal laboratory finding (including ECG finding) that requires an action or intervention by the investigator, or a finding judged by the investigator to represent a change beyond the range of normal physiologic fluctuation, should be reported as an AE.

Adverse events may be treatment emergent (i.e., occurring after initial receipt of investigational product) or nontreatment emergent. A nontreatment-emergent AE is any new sign or symptom, disease, or other untoward medical event that begins after written informed consent has been obtained but before the subject has received investigational product.

Elective treatment or surgery or preplanned treatment or surgery (that was scheduled prior to the subject being enrolled into the study) for a documented pre-existing condition, that did not worsen from baseline, is not considered an AE (serious or nonserious). An untoward medical event occurring during the prescheduled elective procedure or routinely scheduled treatment should be recorded as an AE or SAE. The term AE is used to include both serious and non-serious AEs.

7.1.2 Definition of serious adverse events

A serious adverse event is an AE occurring during any study phase (i.e., screening, run-in, treatment, wash-out, follow-up), at any dose of the study drugs that fulfils one or more of the following criteria:

- Results in death
- Is immediately life-threatening
- Requires in-patient hospitalization or prolongation of existing hospitalization
- Results in persistent or significant disability or incapacity
- Is a congenital abnormality or birth defect in offspring of the subject
- Is an important medical event that may jeopardize the patient or may require medical intervention to prevent one of the outcomes listed above.

Medical or scientific judgment should be exercised in deciding whether expedited reporting is appropriate in this situation. Examples of medically important events are intensive treatment in an emergency room or at home for allergic bronchospasm, blood dyscrasias, or convulsions that do not result in hospitalizations; or development of drug dependency or drug abuse.

The causality of SAEs (their relationship to all study treatment/procedures) will be assessed by the investigator(s) and communicated to AstraZeneca

7.1.3 Definition of adverse events of special interest (AESI)

An AESI is one of scientific and medical interest specific to understanding of the investigational product and may require close monitoring and rapid communication by the investigator to AstraZeneca/Medimmune. An AESI may be serious or nonserious. The rapid reporting of AESIs allows ongoing analysis of these events in order to characterize and understand them in association with the use of this investigational product.

AESIs for durvalumab include but are not limited to events with a potential inflammatory or immune-

mediated mechanism and which may require more frequent monitoring and/or interventions such as steroids, immunosuppressants and/or hormone replacement therapy. These AESIs are being closely monitored in clinical studies with durvalumab monotherapy and combination therapy. An immune-related adverse event (irAE) is defined as an adverse event that is associated with drug exposure and is consistent with an immune-mediated mechanism of action and where there is no clear alternate etiology. Serologic, immunologic, and histologic (biopsy) data, as appropriate, should be used to support an irAE diagnosis. Appropriate efforts should be made to rule out neoplastic, infectious, metabolic, toxin, or other etiologic causes of the irAE.

If the Investigator has any questions in regards to an adverse event (AE) being an irAE, the Investigator should promptly contact the Study Physician.

AESIs observed with durvalumab include:

- Diarrhea/Colitis and intestinal perforation
- Pneumonitis/ILD
- Hepatitis/transaminase increases
- Neuropathy / neuromuscular toxicity (Guillain-Barré, and myasthenia gravis)
- Endocrinopathy (i.e. events of hypophysitis, hypopituitarism adrenal insufficiency, , hyper- and hypothyroidism, and type I diabetes mellitus),
- Rash/Dermatitis
- Nephritis/blood creatinine increases
- Pancreatitis (serum lipase and amylase increases)
- Myocarditis
- Myositis/Polymyositis
- Intestinal perforations

Other inflammatory responses that are rare with a potential immune-mediated aetiology include, but are not limited to:

- Pericarditis
- Sarcoidosis
- Uveitis
- Other events involving the eye and skin
- Hematological events
- Rheumatological events
- Vasculitis
- Non-infectious meningitis
- Non-infectious encephalitis

It is possible that events with an inflammatory or immune mediated mechanism could occur in nearly all organs. In addition, infusion-related reactions and hypersensitivity/anaphylactic reactions with a different underlying pharmacological etiology are also considered AESIs.

Further information on these risks (e.g. presenting symptoms) can be found in the current version of the durvalumab Investigator Brochure.

7.1.4 Pneumonitis

Adverse events of pneumonitis are of interest for AstraZeneca/Medimmune, as pneumonitis has been reported with anti-PD-1 MAb⁵¹. Initial work-up should include high-resolution CT scan, ruling out infection, and pulse oximetry. Pulmonary consultation is highly recommended.

Guidelines for the management of subjects with immune-mediated events including pneumonitis are outlined in Appendix B, Table 1.

7.1.5 Hypersensitivity reactions

Hypersensitivity reactions as well as infusion-related reactions have been reported with anti PD-L1 and anti-PD-1 therapy^{51, 69}. As with the administration of any foreign protein and/or other biologic agents, reactions following the infusion of MAb can be caused by various mechanisms, including acute anaphylactic (immunoglobulin E-mediated) and anaphylactoid reactions against the MAb, and serum sickness. Acute allergic reactions may occur, may be severe, and may result in death. Acute allergic reactions may include hypotension, dyspnea, cyanosis, respiratory failure, urticaria, pruritus, angioedema, hypotonia, arthralgia, bronchospasm, wheeze, cough, dizziness, fatigue, headache, hypertension, myalgia, vomiting and unresponsiveness.

Guidelines for management of subjects with hypersensitivity (including anaphylactic reaction) and infusion related reactions are outlined in Appendix B, Table 1.

7.1.6 Hepatic function abnormalities (hepatotoxicity)

Increased transaminases have been reported during treatment with anti-PD-L1/anti-PD-1 antibodies⁶⁹. Inflammatory hepatitis has been reported in 3% to 9% of subjects treated with anti CTLA-4 monoclonal antibodies (e.g., ipilimumab). The clinical manifestations of ipilimumab-treated subjects included general weakness, fatigue, nausea and/or mild fever and increased liver function tests such as AST, ALT, alkaline phosphatase, and/or total bilirubin.

Hepatic function abnormality is defined as any increase in ALT or AST to greater than $3 \times$ ULN and concurrent increase in total bilirubin to be greater than $2 \times$ ULN. Concurrent findings are those that derive from a single blood draw or from separate blood draws taken within 8 days of each other.

Follow-up investigations and inquiries will be initiated promptly by the investigational site to determine whether the findings are reproducible and/or whether there is objective evidence that clearly supports causation by a disease (e.g., cholelithiasis and bile duct obstruction with distended gallbladder) or an agent other than the investigational product. Guidelines for management of subjects with hepatic function abnormality are outlined in Appendix B, Table 1.

Cases where a subject shows an AST or ALT $\geq 3 \times$ ULN or total bilirubin $\geq 2 \times$ ULN may need to be reported as SAEs. These cases should be reported as SAEs if, after evaluation they meet the criteria for a Hy's Law case or if any of the individual liver test parameters fulfill any of the SAE criteria.

Criteria for Hy's Law (FDA Guidance 2009)

- The drug causes hepatocellular injury, generally shown by a higher incidence of 3 fold or greater elevations above the ULN of ALT or AST
- Among trial subjects showing such aminotransferase elevations, often with aminotransferases much greater than $3 \times$ ULN, one or more also show elevation of serum total bilirubin to $>2 \times$ ULN, without initial findings of cholestasis (elevated serum alkaline phosphatase)
- No other reason can be found to explain the combination of increased aminotransferases and total bilirubin, such as viral hepatitis A, B, or C; pre-existing or acute liver disease; or another drug capable of causing the observed injury.

7.1.7 Gastrointestinal disorders

Diarrhea/colitis is the most commonly observed treatment emergent SAE when tremelimumab is used as monotherapy. In rare cases, colon perforation may occur that requires surgery (colectomy) or can lead to a fatal outcome if not properly managed. Guidelines on management of diarrhea and colitis in patients receiving durvalumab are provided in Table 1.

7.1.8 Endocrine disorders

Immune-mediated endocrinopathies include hypophysitis, adrenal insufficiency, and hyper- and hypothyroidism. Guidelines for the management of patients with immune-mediated endocrine events are provided in Table 1.

7.1.9 Pancreatic disorders

Immune-mediated pancreatitis includes autoimmune pancreatitis, and lipase and amylase elevation. Guidelines for the management of patients with immune-mediated pancreatic disorders are provided in Table 1.

7.1.10 Neurotoxicity

Immune-mediated nervous system events include encephalitis, peripheral motor and sensory neuropathies, Guillain-Barré, and myasthenia gravis. Guidelines for the management of patients with immune-mediated neurotoxic events are provided in Table 1.

7.1.11 Nephritis

Consult with Nephrologist. Monitor for signs and symptoms that may be related to changes in renal function (e.g. routine urinalysis, elevated serum BUN and creatinine, decreased creatinine clearance, electrolyte imbalance, decrease in urine output, proteinuria, etc). Patients should be thoroughly evaluated to rule out any alternative etiology (e.g., disease progression, infections etc.). Steroids should be considered in the absence of clear alternative etiology even for low grade events (Grade 2), in order to prevent potential progression to higher grade event. Guidelines for the management of patients with immune-mediated neurotoxic events are provided in Table 1.

7.1.12 Radiation Risks

This is a non-ablative subclinical radiation dose that is expected to be associated with minimal or no risk.

7.2 Assessment of safety parameters

7.2.1 Adverse Event Characteristics

CTCAE term (AE description) and grade: The descriptions and grading scales found in the revised NCI Common Terminology Criteria for Adverse Events (CTCAE) version 4.0 will be utilized for AE reporting. A copy of the CTCAE version 4.0 can be downloaded from the CTEP web site (<http://ctep.cancer.gov>).

Attribution of the AE:

- Definite – The AE is clearly related to the study treatment.
- Probable – The AE is likely related to the study treatment.
- Possible – The AE may be related to the study treatment.
- Unlikely – The AE is doubtfully related to the study treatment.
- Unrelated – The AE is clearly NOT related to the study treatment.

7.3 Recording of Adverse Events

All adverse events will be recorded on a patient specific adverse event log. The AE log will be maintained by the research staff and kept in the patient's research chart.

Adverse events will be recorded using a recognized medical term or diagnosis that accurately reflects the event. Adverse events will be assessed by the investigator for severity, relationship to the investigational product, possible etiologies, and whether the event meets criteria of an SAE and therefore requires immediate notification to AstraZeneca/MedImmune Patient Safety.

The following variables will be collected for each AE:

- AE (verbatim)
- The date when the AE started and stopped
- Changes in NCI CTCAE grade and the maximum CTC grade attained

- Whether the AE is serious or not
- Investigator causality rating against durvalumab (yes or no)
- Action taken with regard to durvalumab
- Outcome

In addition, the following variables will be collected for SAEs as applicable:

- Date AE met criteria for serious AE
- Date Investigator became aware of serious AE
- Reason AE is serious
- Date of hospitalization
- Date of discharge
- Probable cause of death
- Date of death
- Autopsy performed
- Description of AE
- Causality assessment in relation to Study procedure(s)

7.3.1 Study recording period and follow-up for AEs and SAEs

Adverse events and serious adverse events will be recorded from time of signature of informed consent, throughout the treatment period and including the follow-up period (90 days after the last dose of durvalumab or initiation of new anti-cancer therapy, whichever occurs first). During the course of the study all AEs and SAEs should be proactively followed up for each subject. Every effort should be made to obtain a resolution for all events, even if the events continue after discontinuation/study completion.

The investigator is responsible for following all SAEs until resolution, until the subject returns to baseline status, or until the condition has stabilized with the expectation that it will remain chronic, even if this extends beyond study participation.

Follow-up of unresolved adverse events

Any AEs that are unresolved at the subject's last visit in the study are followed up by the investigator for as long as medically indicated, but without further recording in the eCRF. After 90 days, only subjects with ongoing investigational product-related SAEs will continue to be followed for safety. AstraZeneca/MedImmune retains the right to request additional information for any subject with ongoing AE(s)/SAE(s) at the end of the study, if judged necessary.

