5.1 Treatment Plan

Patients with biopsy proven NSCLC clinical stages I (tumors > 2 cm), II, and IIIA will be randomly assigned to 2 preoperative cycles of the anti-PD-L-1 antibody durvalumab followed by surgical resection *or* non-ablative stereotactic radiotherapy given concurrently with the first cycle of the anti-PD-L1 antibody followed by an additional cycle of the antibody alone followed by surgical resection. In both arms of the trial, patients will receive adjuvant durvalumab every 4 weeks for a total of 12 cycles. Patients randomized to the antibody alone arm will receive two cycles of durvalumab at a dose of 1.12 g every three weeks. Patients in the radio-immunotherapy arm will also be treated with two cycles of durvalumab (1.12 g q 3 weeks) plus radiotherapy delivered in 3 daily fraction of 8Gy starting concurrently with the first cycle of durvalumab (see trial schema). This delivered non-ablative radiation dose of 24 Gy is equivalent to a biologically effective dose (BED) of 43.2Gy, which is significantly lower than the standard therapeutic dose for ablation of T1-T2 NSCLC (BED>100Gy). The objective is to induce immunogenic cell death, enhance antigen presentation and increase cytotoxic T lymphocyte activity without tumor ablation. This non-ablative dose of radiation is selected based on the results of studies by one of our co-investigators showing that the 8 Gy_x3 regimen resulted in significant immune modulation in preclinical models (24). A research core biopsy for the collection of tumor tissue is suggested but not mandatory. If a tissue biopsy has already been obtained for diagnostic purposes, a core biopsy may be performed for research purposes only to obtain tumor tissue. If a tissue biopsy has not been performed yet for diagnostic purposes, a core biopsy may be performed for diagnosis and tissue will be obtained for research purposes. Tissue from the preoperative core samples and from the resected surgical specimens will be stored for future correlative studies. Although PDL-1 expression is not required for eligibility, preoperative and post-operative tissue will be stored for future determination of PDL-1 expression. All patients will proceed to surgical resection 2-6 weeks after the second cycle of durvalumab regardless of local response assessment and provided that repeat imaging shows no evidence of systemic disease. Postoperative durvalumab will commence 4-12 weeks postoperatively at a fixed dose of 1.5 g every 4 weeks for 12 cycles. Patients receiving adjuvant chemotherapy may commence adjuvant monthly anti-PD-L1 after completing chemotherapy.

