If the infusion takes longer than 60 minutes then blood pressure and pulse measurements should be collected every 30 minutes (± 5 minutes) and as described above or more frequently if clinically indicated.

^e At screening and at Day 1-baseline, and as clinically indicated. Baseline and abnormal ECG at any time in triplicate, at screening in single. ECGs should be taken within an hour prior to the start of the infusion at Baseline C1D1.

^f If screening laboratory assessments are performed within 7 days prior to Day 1 they do not need to be repeated at Day 1. Results for safety bloods must be available and reviewed before commencing an infusion. Gamma glutamyltransferase (GGT) tested at Screening, Day 1 and as clinically indicated.

^g Free T3 and free T4 will only be measured if TSH is abnormal. They should also be measured if there is clinical suspicion of an adverse event related to the endocrine system.

^h Urinalysis performed at Screening, Day 1, Day 22, every 4 weeks during adjuvant durvalumab treatment, and as clinically indicated.

ⁱ Coagulation tests: prothrombin time, APTT and INR – only performed at Screening and as clinically indicated.

^j Post-operative CT scans are performed every 6 months for 2 years.

^k Subjects in Arm 1 and Arm 2 will receive adjuvant treatment with durvalumab monotherapy at 1.5 g every 4 weeks for 12 cycles starting 4-12 weeks postoperatively, following standard of care postoperative therapy, as required. Refer to Section 8.1.3 for subjects weighing ≤ 30 kg.

^l SBRT 8 Gy will be given on days 1, 2, and 3 only. On day 1, SBRT will be given prior to the durvalumab administration.

^m Surgical resection will take place 2 -6 weeks after the last dose of durvalumab. Tumor, adjacent normal lung, and lymph node specimens will be obtained from the surgical resection specimen, snap frozen.

ⁿ Standard of care CT/PET scans performed prior to obtaining informed consent and within 42 days prior to C1D1 may be used for screening.

Screening laboratory procedures performed within 7 days of Cycle 1 Day 1 (C1D1) do not need to be repeated on C1D1.

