7.3.4 Reporting of SAE to FDA

All SAEs will be reported, whether or not considered causally related to the investigational product, or to the study procedure(s). The investigator is responsible for informing the IRB of the SAE as per section 7.5.2. The reporting period for SAEs is the period immediately following the time that written informed consent is obtained through 90 days after the last dose of durvalumab or until the initiation of alternative anticancer therapy.

The Investigator will inform the FDA, via a MedWatch/AdEERs form, of any serious or unexpected adverse events that occur in accordance with the reporting obligations of 21 CFR 312.32, and will concurrently forward all such reports to AstraZeneca. A copy of the MedWatch/AdEERs report will be faxed to AstraZeneca at the time the event is reported to the FDA. It is the responsibility of the investigator to compile all necessary information and ensure that the FDA receives a report according to the FDA reporting requirement timelines and to ensure that these reports are also submitted to AstraZeneca at the same time.

* A *cover page* should accompany the *MedWatch/AdEERs* form indicating the following:

- “Notification from an Investigator Sponsored Study”
- The investigator IND number assigned by the FDA
- The investigator’s name and address
- The trial name/title and AstraZeneca ISS reference number (ESR-##-#####)

* The investigator will also indicate, either in the SAE report or the cover page, the *causality* of events *in relation to all study medications* and if the SAE is *related to disease progression*, as determined by the principal investigator.

* *Send SAE report and accompanying cover page by way of email to AstraZeneca’s designated mailbox: [contact]*

If a non-serious AE becomes serious, this and other relevant follow-up information will also be provided to AstraZeneca and the FDA.

Serious adverse events that do not require expedited reporting to the FDA still need to be reported to AstraZeneca preferably using the MedDRA coding language for serious adverse events. This information should be reported on a monthly basis and under no circumstance less frequently than quarterly.

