7.4 Data Safety Monitoring Plan

Subjects will be carefully monitored and evaluated for adverse events by history, physical examination, and laboratory investigations prior to their scheduled durvalumab infusion and on a monthly basis after surgical resection for 4 months. All toxicities encountered during the study will be evaluated on an ongoing basis according to the NCI Common Toxicity Criteria version 4.0. All study treatment associated adverse events that are serious, at least possibly related and unexpected, and caused subject harm, will be reported to the IRB. Any modifications necessary to ensure subject safety and decisions to continue, or close the trial to accrual are also discussed during these meetings.

If there are 3 or more postoperative deaths in the first 20 patients this would be considered outside of our historical control, and thus the study would be stopped. The Weill Cornell Medical College DSMC will perform data and safety monitoring for this study every 4 months. The Weill Cornell Medical College DSMC will review interim data to evaluate research subject safety, rates of accrual, and efficacy of the experimental intervention. After each evaluation, the Board will provide the principal investigator with recommendations for protocol modification, continuation or termination.

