A third secondary aim is to determine the safety of 2 cycles of preoperative durvalumab with and without radiation followed by surgery and adjuvant durvalumab for 12 months post-operatively.

The fourth secondary aim (exploratory) is to compare DFS between the two arms; however, this comparison will be for exploratory purposes only (this comparison will not be statistically powered to detect specific differences between the two arms).

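### AE/SAE recording runs from the last durvalumab dose and is not reconciled with the 4-month post-resection evaluation in Section 7.4, so a resected patient who gets no post-operative durvalumab leaves recording 48–76 days after surgery

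*Combined protocol and SAP*

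**What the plan says.** Two clocks govern safety observation.

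**Last-dose clock.**
- Section 7.3.1 records AEs and SAEs from consent, through treatment and "including the follow-up period (90 days after the last dose of durvalumab", "or initiation of new anti-cancer therapy, whichever occurs first".
- Section 7.3.4 sets the SAE reporting period "through 90 days after the last dose of durvalumab or until the initiation of alternative anticancer therapy".
- Section 7.3.5 uses the same 90 days for reporting deaths. Later deaths are documented but not reported as SAEs.
- Table 2 places its AE/SAE assessments at day 30 and months 2 and 3 since the last dose. Month 4 is a phone contact with no AE assessment marked.
- Section 7.3.1 adds: "After 90 days, only subjects with ongoing investigational product-related SAEs will continue to be followed for safety".

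**Surgery clock.** Section 7.4 has subjects evaluated for adverse events before each infusion and "on a monthly basis after surgical resection for 4 months". It does not make this conditional on adjuvant durvalumab being started.

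**Timing of surgery.** Section 5.1 states: "All patients will proceed to surgical resection 2-6 weeks after the second cycle of durvalumab". Table 1, footnote m, states: "Surgical resection will take place 2 -6 weeks after the last dose of durvalumab". The Table 1 grid puts the second dose on Day 22 and surgery on Days 36–69. Post-operative durvalumab starts 4–12 weeks after surgery, or after adjuvant chemotherapy where that is given, for 12 four-weekly cycles (Section 5.1).

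**Use of the data.** The third secondary aim in Section 11.1.2 is to "determine the safety of 2 cycles of preoperative durvalumab with and without radiation followed by surgery" and adjuvant durvalumab. Section 11.2.2 tabulates the frequency of subjects with toxicities in each arm, with exact 95% confidence intervals. It names no observation window.

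**The concern.** Surgery is part of the regimen whose safety is to be described, yet the rules that decide whether an event is recorded take no account of its date. A patient who is resected and then receives no further durvalumab has a last dose that precedes surgery, so part of the 90 days is spent before the operation takes place. A patient who starts adjuvant durvalumab has the clock reset.

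Time under observation after surgery therefore depends on whether a later treatment is started. A proportion of subjects with an event is interpretable only if subjects are observed for comparable periods. Here unequal periods would enter the same table unmarked.

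Section 7.4 appears to supply a common post-surgical period, but it speaks of monitoring and evaluation and does not amend the recording and reporting rules. A site that follows 7.3.1 and a site that follows 7.4 would capture different events for the same patient. The mortality stopping rule in 7.4 (three postoperative deaths among the first 20 patients) also gives no interval for what counts as postoperative.

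**Working it through.** The documents state no figure for post-surgical recording time, so there is none to reproduce. The check is date arithmetic.

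**Inputs.** Recording closes 90 days after the last dose (7.3.1). Surgery is 14–42 days after the last pre-operative dose (5.1; Table 1, footnote m). The Table 1 grid gives dose 2 on Day 22 and surgery on Days 36–69. Adjuvant treatment starts 28–84 days after surgery, with 12 cycles 28 days apart (5.1). Section 7.4 evaluates for 4 months after resection, taken as 4 × 30.4 ≈ 122 days.

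**1. Resected, no post-operative dose, no new therapy.** Days recorded after surgery = 90 − (days from last dose to surgery).
- 2–6 week rule: 90 − 14 = 76; 90 − 42 = 48. **Range 48–76 days.**
- Table 1 grid: 36 − 22 = 14 and 69 − 22 = 47, giving 90 − 14 = 76 and 90 − 47 = 43. **Range 43–76 days.**

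Six weeks after Day 22 is Day 64, so Day 69 does not match the 2–6 week rule and the 43-day figure rests on the grid alone. Footnote m counts from the last dose, so 48–76 days also applies to a patient resected after only one pre-operative dose.

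**2. Patients who start adjuvant durvalumab.** Days recorded after surgery = start + 28 × (cycles − 1) + 90.
- All 12 cycles on schedule: 28 + 308 + 90 = 426; 84 + 308 + 90 = 482. **Range 426–482 days.**
- One cycle only: 28 + 90 = 118; 84 + 90 = 174. **Range 118–174 days.**

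**3. Gap to the Section 7.4 period for a non-starter.**
- 2–6 week rule: 122 − 76 = 46 to 122 − 48 = 74 days, or 46/122 = 38% to 74/122 = 61% of the four months.
- With Day 69: 122 − 43 = 79 days, or 79/122 = 65%.

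**4. Cut-off against the adjuvant start window.** Adjuvant durvalumab may start up to day 84 after surgery. Without a post-operative dose, the 90 days run out 84 − 76 = 8 to 84 − 48 = 36 days before that window closes (84 − 43 = 41 with Day 69). A site can therefore pass the cut-off before it knows whether cycle 2 was the last dose.

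**5. New anti-cancer therapy.** Sections 7.3.1 and 7.3.4 close recording when it starts. Section 5.1 contemplates adjuvant chemotherapy, and neither 7.3.1 nor 7.3.4 says whether that counts. If it does, the intervals in step 1 are upper limits for those patients.

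**The case against.** The strongest reply is that the plan already has a surgery-based safety rule. Section 7.4 requires monthly AE evaluation for 4 months after resection, whether or not adjuvant treatment starts, so it would be wrong to say that all safety assessment is tied to the last dose. That stands, and it is why this is a failure to reconcile two rules rather than a missing rule. It does not remove the problem: 7.4 does not extend recording, and 7.3.1 restricts follow-up after 90 days to ongoing product-related SAEs. A new surgical complication judged unrelated to durvalumab falls outside that.

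Second, the losses are limited. If no new therapy starts, at least the first 43 post-operative days are recorded. SAEs already recorded are followed to resolution or stabilisation (7.3.1), all subjects are followed for survival (5.4.1), and later deaths are documented (7.3.5). A patient with a recorded complication is already counted in the table. All of this stands: what can be lost is new-onset events after about day 48–76 in a subset of patients.

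Third, 7.3.1 also covers the treatment period, so a site might keep recording until a patient is declared off durvalumab. That reading is possible, but the documents do not say so.

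A reader might go further and infer that surgical toxicity is understated in the very patients most likely to have it, or that the comparison is tilted towards SBRT looking safe. The documents support neither. They do not say that non-starters have more complications, and Section 5.4.1 lists several other reasons for stopping durvalumab. A complication that prevents adjuvant treatment must precede that decision, so much of it would fall inside the recorded window. No between-arm difference in non-starting is given, and Section 11.2.2 plans per-arm tabulation, not a test of toxicity between arms.

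**Conclusion.** The point holds as an unreconciled conflict with a practical consequence. Under the stated recording rules, a resected patient with no post-operative durvalumab is observed for 48–76 days after surgery (43 on Table 1's Day 69), against 426–482 days for one who completes adjuvant treatment and about 122 days under Section 7.4. Because Section 11.2.2 has no common window, the safety of the sequence including surgery can be understated through missed late-onset events in non-starters.

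The day counts assume no new anti-cancer therapy; if adjuvant chemotherapy counts as such, the windows are shorter. The number of patients affected is not in the documents. If, as an assumption, 10–30% of 60 resected patients did not start adjuvant durvalumab, that would be 6–18 patients. The number of events missed, and the size and direction of any difference between arms, cannot be derived. This is an inexpensive correction worth making, not a flaw that undermines the trial.

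**What to change.** Align Sections 7.3.1, 7.3.4 and 7.3.5 and Table 2 with Section 7.4:

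1. For every resected patient in both arms, run AE/SAE recording to the later of 90 days after the last durvalumab dose and 4 months after surgery. Add the matching surgery-timed AE assessments to Table 2.
2. State that new anti-cancer therapy, including adjuvant chemotherapy, does not close the post-operative interval, and that its start date is flagged so that later events can be identified.
3. In Section 11.2.2, tabulate post-operative events and deaths by arm over that same fixed 4-month interval for all resected patients, separately from events during adjuvant treatment.
4. State which interval defines a postoperative death for the stopping rule in Section 7.4, and reconcile Table 1's Day 69 with the 2–6 week rule.

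The cost is a short amendment, slightly more AE recording, and one or two extra contacts for patients who do not start adjuvant durvalumab. Some chemotherapy toxicity will enter the post-operative table; the flag allows it to be shown separately.
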